6.21.1. Severity

All AEs, both serious and non-serious, will be assessed for severity using the Common Terminology Criteria for Adverse Events (CTCAE) Version 5.0. The CTCAE scale includes unique clinical descriptions of AEs that are categorized by anatomy and/or pathophysiology and is provided in the Site Operations Manual.

The CTCAE scale displays Grades 1 through 5 with unique clinical descriptions of severity for each AE (including abnormal laboratory values) based on this general guideline provided in the CTCAE scale. For any AEs not covered by CTCAE the conventional definition of severity will be used.

- Grade 1 (Mild) AE: minor; no specific medical intervention; marginal clinical relevance
- Grade 2 (Moderate) AE: minimal intervention; local intervention; noninvasive intervention
- Grade 3 (Severe) AE: significant symptoms requiring hospitalization or invasive intervention;
- Grade 4 (Life-threatening or disabling) AE: Complicated by acute, life-threatening complications; need for intensive care or emergent invasive procedure
- Grade 5 Fatal AE

6.21.2. Relationship

The Investigator or qualified sub-Investigator is responsible for assessing the relationship to study drug using clinical judgment and the following considerations:

- Not related: all AEs should be considered related unless the AE is clearly unrelated to study drug or clearly due to the subject's underlying disease. For a SAE, an alternative causality must be provided (e.g., preexisting condition, underlying disease, intercurrent illness, or concomitant medication).
- Related: There is reasonable possibility that the event may have been caused by the study drug.

Ineffective treatment should not be reported as an AE.

The relationship to study-related procedures (e.g., invasive procedures such as venipuncture or biopsy) should be assessed using the following considerations:

- Not related: Evidence exists that the AE has an etiology other than the study procedure.
- Related: The AE occurred as a result of study procedures.

6.21.3. Overdose

An overdose is any dose of study drug given to a subject that exceeds the protocol specified dose by 10% or more. In the event of an overdose-associated AE, appropriate supportive therapy should be initiated according to the subject's signs and symptoms.

Any overdose, with or without associated AEs, will be promptly reported to the Sponsor and recorded as non-compliance on the eCRF. AEs associated with overdose should be reported on relevant AE/SAE sections in the eCRF.

6.21.4. Serious Adverse Events

6.21.4.1. Definition

A SAE is defined by federal regulation as any AE occurring at any dose that results in any of the following outcomes: death, life-threatening AE, hospitalization or prolongation of existing hospitalization, a persistent or significant incapacity or substantial disruption of the ability to conduct normal life functions, or a congenital anomaly/birth defect.

Important medical events that may not result in death, be life threatening, or require hospitalization may be considered an SAE when, based upon appropriate medical judgment, they may jeopardize the subject, and may require medical or surgical intervention to prevent one of the outcomes listed in this definition. Examples of such medical events include allergic bronchospasm requiring intensive treatment in an emergency room or at home, blood dyscrasias or convulsions that do not result in inpatient hospitalization, or the development of drug dependency or drug abuse.

A life-threatening AE is one that, in the view of the Investigator, places the subject at immediate risk of death from the reaction as it occurred.

An unexpected AE is any event for which the specificity or severity is not consistent with the AE profile in the current EFX IB.

All SAEs, regardless of cause(s) or relationship to study drug, must be reported immediately to the study Sponsor and/or designee.

6.21.5. Reporting Adverse Events

6.21.5.1. Reporting Procedures for Non-Serious Adverse Events

The Investigator is responsible for ensuring that all AEs observed by the Investigator or designee or reported by the subject are reported using the AE eCRF.

The Investigator will assign the following AE attributes:

- AE diagnosis or syndrome(s), if known (if not known, signs or symptoms)
- Dates of onset and resolution (if resolved)
- Severity
- Relatedness to study drug or study-related procedures
- Action taken

Follow-up of non-serious AEs will continue through the last day on the study and/or until a definitive outcome (e.g., resolved, resolved with sequelae, lost to follow-up) is achieved.

When a subject is withdrawn from the study because of a non-serious AE, the Sponsor and/or designee must be notified by e-mail or phone within 48 hours.

6.21.5.2. Reporting Procedures Serious Adverse Events

The Investigator is responsible for ensuring that all SAEs observed by the Investigator or reported by the subject are promptly assessed and reported. The Investigator must assess whether the SAE is related to study drug or any study-related procedure.

The procedures for reporting SAEs are as follows:

Initial Reports

- All SAEs occurring after the first dose of EFX or during the study treatment and safety follow up periods must be reported to Medpace Clinical Safety within 24 hours of the knowledge of the occurrence. After the protocol-specified reporting window, any SAE that the investigator considers related to study must be reported to Medpace Clinical Safety or the Sponsor/designee.
- To report the SAE, complete the SAE form electronically in the electronic data capture (EDC) system for the study. When the form is completed, Medpace Safety personnel will be notified electronically by the EDC system and will retrieve the form. If the event meets serious criteria and it is not possible to access the EDC system, send an email to Medpace Safety at the second series of the second s

or call the Medpace SAE hotline (phone number listed below), and fax/email the completed paper SAE form to Medpace (contact information listed below) within 24 hours of awareness. When the EDC system becomes available, the SAE information must be entered within 24 hours of the system becoming available.

Follow-Up Reports

- The investigator must continue to follow the subject until the SAE has subsided or until the condition becomes chronic in nature, stabilizes (in the case of persistent impairment) or the subject dies.
- Within 24 hours of receipt of follow-up information, the investigator must update the SAE form electronically in the EDC system for the study, and submit any supporting documentation (e.g., subject discharge summary or autopsy reports) to Medpace

Clinical Safety via fax or e-mail. If it is not possible to access the EDC system, refer to the procedures outlined above for initial reporting of SAEs.

• The Sponsor or/or designee may request additional information from the Investigator to ensure the timely completion of accurate safety reports.

The Investigator must take all therapeutic measures necessary for resolution of the SAE. Any medications or therapies necessary for treatment of the SAE must be recorded in the SAE form and the concomitant medication eCRF.

Follow-up of SAEs will continue through the last day on the study and/or until a definitive outcome (e.g., resolved, resolved with sequelae, lost to follow-up, fatal) is achieved.

If a subject becomes pregnant during the study or within the safety follow up period defined in the protocol, the investigator is to stop dosing with study drug(s) immediately and the subject should be withdrawn from the study. Early termination procedures and safety followup should be implemented at that time.

A pregnancy is not considered to be an AE or SAE; however, it must be reported to Medpace Clinical Safety within 24 hours of knowledge of the event. Medpace Clinical Safety will then provide the investigator/site the Exposure In Utero (EIU) form for completion. The investigator/site must complete the EIU form and fax/email it back to Medpace Clinical Safety.

If the female partner of a male subject becomes pregnant while the subject is receiving study drug or within the safety follow up period defined in the protocol, the investigator should notify Medpace Clinical Safety as described above.

The pregnancy should be followed until the outcome of the pregnancy, whenever possible. Once the outcome of the pregnancy is known, the follow-up EIU form should be completed and faxed/emailed to Medpace Clinical Safety. If the outcome of the pregnancy meets the criteria for immediate classification as an SAE (i.e., postpartum complication, spontaneous abortion, stillbirth, neonatal death, or congenital anomaly), the investigator should follow the procedures for reporting an SAE.

Safety Contact Information: Medpace Clinical Safety

Some SAEs will qualify for reporting to the Food and Drug Administration (FDA) as applicable via the MedWatch/CIOMS reporting system in accordance with FDA and other

applicable regulations. The Sponsor or its designee will report SAEs and/or SUSARs as required to regulatory authorities and Investigators in compliance with all reporting requirements according to local regulations and Good Clinical Practice (GCP).

The Investigator will notify the appropriate IRB of SAEs occurring at the study site and other AE reports received from the Sponsor, in accordance with local procedures and statutes. The Investigator or designee at each study site is responsible for submitting Investigational New Drug (IND) safety reports (initial and follow-up) and other safety information (e.g., revised Investigator's Brochure) to the IRB and for retaining a copy in the study files.

6.22. Adverse Events of Special Interest

The Investigator will monitor each subject for clinical and laboratory-evidence for predefined AEs of special interest (AESIs) throughout the subject's participation in this study. The Investigator should treat the AESI according to local standard of care. The following conditions will be monitored as AESIs during this study:

- Injection site reactions
- Diarrhea
- Hypoglycemia

In addition, drug-induced liver injury will be monitored and managed according to Section 6.24.

During the course of the study, additional AESIs may be identified by the Sponsor. The Investigator will assess and record in detail any additional information for AESIs on the AE eCRF form.

6.23. Clinical Laboratory Abnormalities and Other Abnormal Assessments as Adverse Events or Serious Events

Laboratory abnormalities are usually not recorded as AEs or SAEs, however, laboratory abnormalities (e.g., clinical chemistry, hematology, urinalysis) independent of the underlying medical condition that require medical or surgical intervention or lead to investigational medicinal product interruption or discontinuation must be recorded as an AE, as well as an SAE, if applicable. In addition, laboratory or other abnormal assessments (e.g., electrocardiogram, X-rays, vital signs) that are associated with signs and/or symptoms must be recorded as an AE or SAE if they meet the definition of an AE (or SAE) as described in Section 6.21. If the laboratory abnormality is part of a syndrome, record the syndrome or diagnosis (e.g., anemia) not the laboratory result (i.e., decreased hemoglobin). Severity should be recorded and graded according to the CTCAE Version 5.0. For AEs associated with laboratory abnormalities, the event should be graded based on the clinical severity in the context of the underlying conditions; this may or may not be in agreement with the grading of the laboratory abnormality.

Toxicity Management

Any questions regarding toxicity management should be directed to the Medical Monitor.

Grade 1 and 2 Laboratory Abnormality or Clinical Event

Continue investigational medicinal product at the discretion of the Investigator.

Grade 3 Laboratory Abnormality or Clinical Event

- For Grade 3 clinically significant laboratory abnormality or clinical event, investigational medicinal product may be continued if the event is considered to be unrelated to investigational medicinal product.
- For a Grade 3 clinical event, or clinically significant laboratory abnormality confirmed by repeat testing, that is considered to be related to investigational medicinal product, investigational medicinal product should be withheld until the toxicity returns to ≤ Grade 2.
- If a laboratory abnormality recurs to ≥ Grade 3 following re-challenge with investigational medicinal product and is considered related to investigational medicinal product, then investigational medicinal product should be permanently discontinued, and the subject managed according to local practice. Recurrence of laboratory abnormalities considered unrelated to investigational medicinal product may not require permanent discontinuation.

Grade 4 Laboratory Abnormality or Clinical Event

- For a Grade 4 clinical event or clinically significant Grade 4 laboratory abnormality confirmed by repeat testing, the DMC should perform a causality assessment. The study drug may be restarted if the DMC concludes that the AE or laboratory abnormalities were not related to study drug, the AE has resolved, laboratory abnormalities have returned to baseline, and the subject is amenable to close clinical follow-up.
- If a laboratory abnormality recurs to ≥ Grade 4 following re-challenge with investigational medicinal product and is considered related to investigational medicinal product, then investigational medicinal product should be permanently discontinued, and the subject managed according to local practice. Recurrence of laboratory abnormalities considered unrelated to investigational medicinal product may not require permanent discontinuation.
- If, after re-challenge, a subject has a second serious AE or recurrent elevations (even mild or minimal) of total bilirubin, ALT, or AST as defined in Section 6.19, study drug should be discontinued permanently.

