6.19. Criteria for Discontinuation of Study Drug

Study drug must be discontinued in the following instances:

- Liver transplantation
- Subject develops an SAE consisting of a serious hypersensitivity reaction to study drug
- Subject experiences diarrhea that meets the criteria in Section 6.23 for discontinuation.
- Subject experiences a Grade IV Common Terminology Criteria for Adverse Events (CTCAE) or meets the criteria for Drug Induced Liver Injury described in Section 6.24.
 - The Data Monitoring Committee (DMC) should perform a causality assessment. The study drug may be restarted if the DMC concludes that the AE or laboratory abnormalities were not related to study drug, the AE has resolved, laboratory abnormalities have returned to baseline, and the subject is amenable to close clinical follow-up.
 - If, after re-challenge, a subject has a second serious AE or recurrent elevations (even mild or minimal) of total bilirubin, ALT, or AST as defined in Section 6.24.3, study drug should be discontinued permanently.
- Intercurrent illness that would, in the judgment of the Investigator, affect assessments of clinical status to a significant degree. Following resolution of intercurrent illness, the subject may resume study dosing at the discretion of the Investigator, in consultation with the Medical Monitor
- Unacceptable toxicity or toxicity that, in the judgment of the Investigator, compromises the ability to continue study-specific procedures or is considered to not be in the subject's best interest
- Subject or Investigator request to discontinue for any reason
- Significant subject noncompliance
- Significant protocol violation that impacts subject safety

- Pregnancy during the study; refer to Appendix C.
- Discontinuation of the study at the request of Akero, a regulatory agency, or an IRB/IEC/EC.

Cohort C

In addition to the above criteria, study drug must be discontinued in the following instances in Cohort C:

- Development of any decompensation events including ascites, hepatic encephalopathy (HE), or variceal bleeding
- Progression to Child Pugh Class C

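### Protocol 6.19 and 6.23 differ on whether a Grade 4 laboratory value must be confirmed before study drug stops, and the two recurrence bullets in 6.23 do not fit together

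*Protocol*

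**What the plan says.** Protocol 6.19 opens with "Study drug must be discontinued in the following instances", and one entry reads "Subject experiences a Grade IV Common Terminology Criteria for Adverse Events (CTCAE) or meets the criteria for Drug Induced Liver Injury". No repeat test is attached to it. The text beneath asks the DMC to assess causality and provides for a return to dosing: "The study drug may be restarted if the DMC concludes that the AE or laboratory abnormalities were not related to study drug", subject also to resolution, return to baseline and close follow-up. Laboratory values fall within the grading system, since Protocol 6.21.1 states: "The CTCAE scale displays Grades 1 through 5 with unique clinical descriptions of severity for each AE (including abnormal laboratory values".

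Protocol 6.23 (Toxicity Management, Grade 4) says: "For a Grade 4 clinical event or clinically significant Grade 4 laboratory abnormality confirmed by repeat testing, the DMC should perform a causality assessment". The same restart conditions follow. Nothing there says that drug is stopped or held beforehand. The Grade 3 entry, by contrast, does say that drug is withheld for a related event until it falls to Grade 2 or below.

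On recurrence judged related to study drug, 6.23 requires permanent discontinuation in two places. Under the Grade 3 heading the condition is "If a laboratory abnormality recurs to ≥ Grade 3 following re-challenge". Under the Grade 4 heading it is "If a laboratory abnormality recurs to ≥ Grade 4 following re-challenge". A further bullet, also in 6.19, requires permanent discontinuation after re-challenge for a second serious adverse event or for any recurrent rise in total bilirubin, ALT or AST, however small.

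**The concern.** Two sections govern the same decision and do not describe it alike. A Grade 4 laboratory value awaiting its repeat test is a mandatory stop in 6.19 and has not yet started any process in 6.23. Dosing is weekly, and 6.23 sets no deadline for the repeat (6.24.1 does set one for liver tests), so the next dose can fall due before confirmation.

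The recurrence bullets raise a second question. If each heading refers to the grade of the first event, a subject who began with Grade 4 has a higher threshold for permanent discontinuation than one who began with Grade 3, and no reason is given.

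Patient safety comes first, but the analysis is touched too. Under 6.23, a laboratory abnormality that is independent of the underlying condition and leads to interruption or discontinuation must be recorded as an adverse event. Protocol 7.7.2 and SAP 3.5.1 count any adverse event leading to premature discontinuation as treatment-emergent. The section a site follows can therefore alter event and discontinuation counts, which bear directly on Cohort C's primary objective of safety and tolerability. Discontinuation also leads to the early termination visit (Protocol 3.4). At that visit MRI-PDFF is at the investigator's discretion in the Main Study (Appendix A), and FibroScan is not scheduled in Cohort C (Appendix B).

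**Working it through.** No sample size, power or error rate is involved. The check applies each rule to the same result. The inputs are Protocol 6.19, 6.21, 6.21.1, 6.23, 6.24.1 and 6.24.2, and the CTCAE Version 5.0 table in SAP 3.5.2.

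| Case | Under 6.19 | Under 6.23 | Same? |
|---|---|---|---|
| A. Grade 4 value other than ALT, judged clinically significant, repeat pending | Must stop | Process not started; next dose not addressed | No |
| B. Grade 4 value, clinically significant and confirmed | Stop, then DMC review | DMC review; stop implied by the restart provision | In effect, yes |
| C. Grade 4 value, not judged clinically significant | Not an adverse event under 6.21, so arguably not triggered | Not triggered | Largely yes |
| D. First Grade 4, restart, then any recurrent ALT, AST or total bilirubin elevation, or a second serious adverse event | Permanent stop | Permanent stop | Yes |

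**Trigger.** Only case A separates the sections. ALT is set apart because 6.24 has its own stops, with no repeat-test condition attached: above 8 × ULN with normal baseline tests, or above 5 × baseline or 400 U/L with elevated baseline tests. Grade 4 ALT in the SAP table is above 20 × ULN (normal baseline) or above 20 × baseline (abnormal baseline). Since 20 > 8 and 20 > 5, a Grade 4 ALT value has already passed the 6.24 stop.

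**Recurrence.** Take a first Grade 4 abnormality in a test other than ALT, AST or total bilirubin. The DMC finds it not related and drug is restarted. It then recurs at Grade 3, is not serious, and is now judged related. Section 6.23 offers three answers:

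1. Grade 4 recurrence bullet: threshold not reached, because 3 < 4.
2. Grade 3 recurrence bullet, read literally: permanent discontinuation, because 3 ≥ 3 and the bullet does not restrict the grade of the first event.
3. General Grade 3 rule for a related, clinically significant and confirmed abnormality: withhold until Grade 2 or below.

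If answer 2 governs, every recurrence meeting the Grade 4 bullet already meets the Grade 3 bullet, so the Grade 4 bullet adds nothing. If the headings refer to the first event, answer 1 applies and the looser threshold follows the more severe first event. The text does not settle which is meant.

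**Reach.** Outside ALT, AST and total bilirubin, the SAP table gives Grade 4 laboratory ranges for ALP, creatinine, CPK, potassium, amylase, glucose, GGT, neutrophils, white cells and platelets, among others. That table grades Cohort C data for analysis and is not a site management tool, so it only shows where a Grade 4 value is possible.

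**Scale.** One affected subject is 1/20 = 5% of a planned 20-subject arm, or 1/10 = 10% of the planned Cohort C placebo arm. This is the weight of one subject, not a forecast.

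**The case against.** A reader might infer that sites cannot obey both sections. The documents do not support that. Section 6.23 never tells a site to keep dosing on an unconfirmed Grade 4 value. A site that stops under 6.19, repeats the test and refers the case to the DMC breaches neither section. What stands is narrower: a site reading 6.23 alone is not told to stop.

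A reader might also infer that 6.19 disregards clinical significance. It is triggered by an adverse event grade, and 6.21 makes an out-of-range laboratory value an adverse event only if the investigator considers it clinically significant. Section 6.23 adds that the event's grade may differ from the laboratory grade. That largely closes this half of the difference. It leaves the repeat test untouched.

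It can be said that the laboratory abnormalities in the 6.19 restart text refer only to drug-induced liver injury, which shares the same entry. That is possible, but 6.21.1 places abnormal laboratory values within CTCAE grading generally, and 6.19 does not limit its Grade IV trigger to clinical events.

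On recurrence, the literal reading of the Grade 3 bullet removes the anomaly, the scenario needs causality to move from not related to related, and the override covers ALT, AST, total bilirubin and second serious events. All of this is right and narrows the point. It does not remove it: the Grade 4 recurrence bullet itself presupposes a later judgement of related, and on the literal reading that bullet has no function.

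Finally, 6.23 directs toxicity questions to the Medical Monitor. Advice on individual cases does not align the written rules.

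**Conclusion.** The inconsistency is real but limited. Sections 6.19 and 6.23 differ on whether a Grade 4 laboratory value must be confirmed before anything happens, and 6.23 leaves dosing status during the wait unstated. For confirmed, clinically significant Grade 4 values the two sections come to the same result. The recurrence bullets in 6.23 are either redundant or looser after a more severe first event, and only for the narrow sequence worked through above. Even there, a related, confirmed and clinically significant Grade 3 recurrence would still be withheld under the general Grade 3 rule. The difference is between permanent discontinuation and a hold, not between stopping and dosing straight on.

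The conclusion assumes that the Grade IV trigger in 6.19 includes laboratory values judged clinically significant, as 6.21 and 6.21.1 together indicate. The documents give no Grade 4 rate, so no expected count, and no expected effect on the efficacy data, can be stated. The point deserves correction because it concerns when treatment stops and how discontinuations are counted. It does not show that either section's clinical rule is wrong.

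**What to change.** Reconcile the passages:

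- Give 6.19 and 6.23 the same trigger for a Grade 4 laboratory value, saying whether confirmation by repeat testing and clinical significance are required.
- State in both whether study drug is given, held or discontinued while the repeat test and the DMC assessment are pending.
- Replace the two related-recurrence bullets in 6.23 with one rule that expressly covers a first Grade 3 and a first Grade 4 event.
- In the same edit, repair the cross-references. For recurrent liver test elevations, 6.23 points to 6.19 and 6.19 points to 6.24.3, which lists observation steps and defines no such elevation. Section 6.19 also refers to diarrhea criteria in 6.23 that are not there.

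The content of each rule is a clinical decision for the sponsor and DMC. The cost is protocol wording in two sections, with no new assessments.
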